#### **3.3 Safety Endpoints**

Safety endpoints are:

- Incidence and severity of AEs
  - Oral temperatures
  - Use of antipyretics and bronchodilators
  - Hospital length of stay, and ICU length of stay
-

## 4 STUDY PLAN

### 4.1 Study Design

This is an exploratory Phase 2 clinical study to evaluate the protective effects of NasoVAX in patients with early COVID-19. Approximately 96 ambulatory patients with COVID-19, with one or more symptom(s) of fever, cough, and/or shortness of breath, onset of these symptoms within 72 hours of screening, and a PCR-based or rapid antigen test diagnostic, will be enrolled in 3 successive cohorts defined by age and risk factors for severe COVID-19 ([Exclusion Criterion 5](#)) (Cohort 1, ages 18-49 years and risk factors disallowed; Cohort 2, ages 18 and above and risk factors disallowed; and Cohort 3, ages 18 and above and risk factors allowed) of approximately 20, 28, and 48 patients, respectively. The cohorts will be enrolled in ascending order, with Cohort 1 preceding Cohort 2, and Cohort 2 preceding Cohort 3. Cohort 2 will be stratified by age groups of 18-64 years and 65 years and above, whereas Cohort 3 will be stratified by age groups (ages 18-64 years, ages 65 and above) and co-morbidity (one or more risk factors present, no risk factors present).

Study conduct will be overseen by a Data Monitoring Committee (DMC), which will monitor the safety of study participants and review safety data real-time during the course of the study. If any of the Stopping Rules ([Section 7.2](#)) are met, enrollment and study drug treatment will be temporarily halted pending DMC review.

Once a cohort is fully enrolled, enrollment will be paused until all patients either complete 14 days of home assessments or they are determined to have been hospitalized. The DMC will then review the safety and tolerability data and make a recommendation regarding whether to progress to the next cohort. The DMC may unblind the data in conducting its assessments although treatment allocation will not be revealed to operational study personnel.

Upon signing informed consent, patients will undergo Screening assessments at the study center, as per the Schedule of Events ([Table 1](#)). Within each cohort, patients who are determined to be eligible will be randomized that same day (Day 1) in a 1:1 ratio to receive either NasoVAX or placebo with approximately 10 and 14 patients in Cohorts 1 and 2, respectively, receiving NasoVAX and 10 and 14 receiving placebo in Cohorts 1 and 2, respectively. Approximately 24 patients will receive NasoVAX and 24 will receive placebo in Cohort 3.

Study drug will be administered as a single intranasal dose of 0.5 mL (0.25 mL each nostril) in the supine position after which patients must remain in the supine position for 30 minutes. Patients will be observed for at least 2 hours post intranasal administration. Patients who are randomized will be considered enrolled in the study.

No in-person visits are expected during the study after Day 1 unless a participant experiences a change in symptoms or AE that requires a visit for assessment.

---

Prior to discharge from the study center on Day 1, patients will be provided with:

- A fingertip pulse oximetry device connecting to a tablet that will be supplied to the patient to measure resting SpO2 and resting pulse rate remotely. Patients will be trained on the use of the device and tablet
- A digital thermometer for measurement of oral temperature
- Instructions regarding how to take the above measurements and access and complete a web-based electronic diary (eDiary)

After discharge on Day 1, patients will return home for the duration of the study. Patients are to measure resting SpO2, resting pulse rate and oral temperature twice daily at 09:00 hours and 16:00 hours, with a 1-hour window around each time point, and at any time they experience worsening symptoms until Day 14 or hospitalization, whichever comes first. Patients are to record COVID-19-related symptoms daily during this same time period. Study center personnel will contact patients daily by telephone during this period to document the patient's clinical status, record concomitant medications and monitor for AEs.

After Day 14, study center personnel will contact patients via telephone approximately every 7±2 days for 14 additional days to determine if they were hospitalized and to follow AEs that were not resolved by Day 14. If the patient is hospitalized at any time, the dates and times of hospital admission/discharge, ICU admission/discharge, and ventilation requirement are to be recorded, as applicable. Patients who remain hospitalized at the end of 28 days will be followed through Day 42 or death, whichever is sooner. If a patient is discharged and then readmitted before Day 42, he/she will be followed until Day 42.

#### **4.2 Rationale for Study Design**

Several design features are employed in the current study in an effort to minimize bias, including a double-blind design, with patients randomly assigned to NasoVax or placebo on a 1:1 basis. Random assignment of patients avoids bias and helps ensure that both known and unknown risk factors are distributed evenly between treatment groups. The use of placebo control permits prospective comparison between the active treatment group and the control group.

In order to mitigate the risk of exposure to SARS-CoV-2 at the study center and reduce the use of personal protective equipment, all data after administration of study drug will be collected remotely, either electronically or via telephone; no in-person visits post-vaccination are required unless a participant experiences a change in symptoms or AE that requires a visit for assessment. After study drug administration on Day 1, patients will be evaluated remotely.

The study design adheres to the March 2020 FDA Guidance on the conduct of clinical trials during the COVID-19 pandemic (Centers for Disease Control and Prevention, Coronavirus Disease 2019 (COVID-19): Groups at Higher Risk for Severe Illness, Updated May 14,

---

2020 <https://www.cdc.gov/coronavirus/2019-ncov/need-extra-precautions/groups-at-higher-risk.html#serious-heart-conditions> (last accessed June 7, 2020)

United States Food and Drug Administration (2020).

To ensure further the safety of participating patients, a DMC will review safety data after each cohort is enrolled and throughout the study. If any safety concerns are identified, the DMC will make a determination regarding continuation of the study; the DMC may be unblinded for this review. The DMC will oversee all aspects of the study to optimize the safety of study participants. Stopping Rules have also been developed for the further protection of patients.

### **4.3 Rationale for Study Population**

The model of lethal influenza challenge in mice recapitulates the key sequela associated with human infection with COVID-19 disease, including severe disease and death associated with massive lung inflammation and significant elevation in lung inflammatory cytokines. The ability of RD-Ad5 vectors to significantly decrease inflammatory cytokines, lung inflammation and morbidity following viral challenge in mice may be directly relevant to the treatment of COVID-19.

Preclinical data show that intranasal administration of RD-Ad5 vectors, either harboring a transgene or not, can protect mice from lethal challenge with a respiratory pathogen when administered as a single intranasal dose within 2 days and up to 47 days before a lethal challenge with a respiratory pathogen. These observations support the use of NasoVAX or RD-Ad5 vectors in patients with recent or early COVID-19.

To enhance the safety of study participants, the study will be enrolled in cohorts of increasing age and increasing risk for complications of COVID-19. Patients with risk factors for severe COVID-19 will be excluded from Cohort 1. Based on ongoing review of efficacy and safety data, the DMC may remove part or all of these risk factors if preliminary data show no signal for adverse or paradoxical effects.

[figure not shown]
Because the cooperation of the patients is essential for the proper conduct of the study, patients themselves must provide written informed consent before the performance of any study-related procedures, and surrogate consent by family members, designated legal representatives, or caregivers will not be permitted.

Hydroxychloroquine and chloroquine are excluded because these medications are known to acidify vesicles that may prohibit the entry of viruses like RD-Ad5 into respiratory mucosal cells. The half-lives of these agents are 22 and 55 days, respectively, and the periods of exclusion are based on 5 half-lives. The use of these agents is only permitted by the United States (US) Food and Drug Administration under Emergency Use Authorization in the hospital setting, so they are also not allowed in this study as rescue medications for patients with progressive symptoms in the outpatient setting.

---

While remdesivir use is not prohibited, it is not expected to interfere with study conduct, since it is an intravenous medication, the use of which would be restricted to hospitalized patients with severe forms of COVID-19.

#### **4.4 Dose Rationale**

#### **4.5 Schedule of Events**

The schedule for study activities is presented in [Table 1](#).

**Table 1 Schedule of Events – Screening and Treatment Periods**

Procedure	Study Visit Type / Day			
	Screening	Study Drug Treatment	Diary Completion/ Telephone Contact	Telephone Contact
	Study Center Visit		Remote Visit	
	Day 1 Pre-Dose	Day 1	Daily Days 1 to 14	Days 21 and 28 ±2 days
Informed consent	X			
Eligibility criteria check	X			
Demographics	X			
Medical history	X			
Focused cardiovascular and respiratory physical examination	X			
Height and weight	X			
Blood pressure and respiratory rate	X			
Urine pregnancy test a	X			
Randomization	X			
Study drug administration b		X		
Resting SpO 2 c	X		X d	
Resting pulse rate c	X		X d	
Oral temperature c	X		X d	
Baseline/Concomitant medications	X		X	X
AEs			X	X
eDiary completion for COVID-19 symptoms e	X		X	
Criteria for the Assessment of Severity of Illness in Patients with COVID-19 f	X			X
Daily telephone contact to document concomitant medications, clinical and hospitalization status and AEs g			X	
Follow-up contact for hospitalization status, COVID-19 outcomes, and AEs h				X

a For women of child-bearing potential only. Results must be available and confirmed to be negative before study drug administration.

b Study drug is to be administered with the patient in the supine position. The patient is to remain in the supine position for 30 minutes thereafter and be observed for at least 2 hours post intranasal administration.

c To be measured remotely daily at 09:00 and 16:00 hours or at any time the patient experiences worsening symptoms using the study-supplied devices and recorded in the eDiary. Resting SpO2 and pulse are to be measured at rest for 2 minutes. A ±1 hour window will be allowed. On Day 1, only the afternoon (16:00 hours) measurement is required and may be measured at the study center or remotely.

d If the Screening visit occurs in the morning, the patient will be responsible for recording the 16:00 measurements at home later that day; if the visit occurs after 16:00, measurements will commence at home the following morning.

- e The following symptoms will be recorded: fatigue, chills, headache, cough (with or without sputum production), myalgia, sore throat, shortness of breath, nasal congestion, diarrhea, and nausea or vomiting.
  - f After Screening, the patient will be assessed at different timepoints over the course of the trial. The final determination will be made on Day 28 in patients who are not hospitalized and Day 42 in patients who are hospitalized.
  - g Telephone calls to the patient will commence on Day 2. The script for these calls is provided in [Appendix A](#).
  - h The script for the Day 21 and Day 28 phone calls is provided in [Appendix B](#). For hospitalized patients, the dates and times of hospital admission/discharge, date and time of intensive care unit admission/discharge, and ventilation requirement are to be recorded, as applicable. Patients who remain hospitalized at the end of 28 days will be followed through Day 42 or death, whichever is sooner.
-

## 5 POPULATION

### 5.1 Number of Patients

Approximately 96 ambulatory patients with COVID-19, with one or more symptom(s) of fever, cough, or shortness of breath, onset of these symptoms within 72 hours of screening, and a confirmation of SARS-CoV-2 infection by a polymerase chain reaction (PCR)-based or rapid antigen test diagnostic, will be enrolled at up to 12 study centers in the US.

### 5.2 Inclusion Criteria

Patients who meet all of the following criteria are eligible for participation in the study.

1. Able and willing to provide informed consent

Patients themselves must provide written informed consent before the performance of any study-related procedures, and surrogate consent by family members, designated legal representatives, or caregivers will not be permitted.

2. Men and women 18 years of age and older

3. Early COVID-19, defined as one or more symptom(s) of fever (oral temperature  $\geq 100.4^{\circ}\text{F}$ ), cough or shortness of breath, onset of these symptoms within 72 hours of screening, and confirmation of SARS-CoV-2 infection by a PCR-based or rapid antigen test diagnostic

4. Resting  $\text{SpO}_2 \geq 96.0\%$  on room air on two successive measurements

5. For women of childbearing potential (women who are not permanently sterile [documented hysterectomy, bilateral tubal ligation, salpingectomy, or oophorectomy], postmenopausal [12 months with no menses without an alternative medical cause] or in monogamous same-sex relationships)

- Negative urine pregnancy test at Screening
- Willingness to practice a highly effective method of contraception that includes, but is not limited to, abstinence, sex only with persons of the same sex, monogamous relationship with a postmenopausal partner, monogamous relationship with vasectomized partner, vasectomy, licensed hormonal methods, intrauterine device, or consistent use of a barrier method (eg, condom, diaphragm) with spermicide for 28 days after the last dose of study drug

6. For men with sexual partners of childbearing potential, willingness to practice a highly effective method of contraception, as defined above, for 45 days after the last dose of study drug

---

7. Ability and willingness to comply with all aspects of the study, including reliable internet access, through the entire study period

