**Inclusion Criteria:**

1. Able and willing to provide informed consent  
Patients themselves must provide written informed consent before the performance of any study-related procedures, and surrogate consent by family members, designated legal representatives or caregivers will not be permitted.
2. Men and women 18 years of age and older
3. Early COVID-19, defined as one or more symptom(s) of fever (oral temperature  $\geq 100.4^{\circ}\text{F}$ ), cough or shortness of breath, onset of these symptoms within 72 hours of screening, and confirmation of SARS-CoV-2 infection by a polymerase chain reaction (PCR)-based or rapid antigen test diagnostic
4. Resting  $\text{SpO}_2 \geq 96.0\%$  on room air on two successive measurements
5. For women of childbearing potential (women who are not permanently sterile [documented hysterectomy, bilateral tubal ligation, salpingectomy, or oophorectomy] or postmenopausal [12 months with no menses without an alternative medical cause])
  - Negative urine pregnancy test at Screening
  - Willingness to practice a highly effective method of contraception that includes, but is not limited to, abstinence, sex only with persons of the same sex, monogamous relationship with a postmenopausal partner, monogamous relationship with vasectomized partner, vasectomy, licensed hormonal methods, intrauterine device, or consistent use of a barrier method (eg, condom, diaphragm) with spermicide for 28 days after the last dose of study drug
6. For men with sexual partners of childbearing potential, willingness to practice a highly effective method of contraception, as defined above, for 45 days after the last dose of study drug
7. Ability and willingness to comply with all aspects of the study, including reliable internet access, through the entire study period

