### **5.3 Exclusion Criteria**

Patients meeting any of the following criteria are not eligible for participation in the study:

1. Pregnant or lactating women or planning to conceive a child during the next 3 months
2. Resting respiratory rate >20 breaths/min on room air or resting pulse rate  $\geq$  125 beats per minute
3. A rapidly worsening course that in the opinion of the Investigator or treating medical practitioner would lead to hospitalization within the next 24-48 hours
4. Any chronic pulmonary disease, including chronic obstructive pulmonary disease and asthma, or other respiratory diseases that could exacerbate independent of COVID-19
5. The following risk factors for severe COVID-19 (Cohorts 1 and 2 only) ([Centers for Disease Control 2020](#)):
  - a. Severe obesity, defined as body mass index  $\geq$  40 kg/m^2
  - b. History of
    - i. Severe cardiovascular disease, including but not limited to congestive heart failure, coronary artery disease, congenital heart disease, cardiomyopathies, or pulmonary hypertension
    - ii. Diabetes mellitus
    - iii. Chronic or current vaping or cigarette smoking
    - iv. Chronic kidney disease requiring dialysis
    - v. Chronic liver disease, including but not limited to chronic viral hepatitis, non-alcoholic steatohepatitis, or cirrhosis of any cause
    - vi. Hemoglobin disorder, including sickle cell disease and thalassemia

Based on ongoing review of efficacy and safety data, the DMC may remove part or all of these risk factors if preliminary data show no signal for adverse or paradoxical effects.

6. History of Bell's Palsy
-

[figure not shown]

7. Nasal conditions that might affect the suitability of intranasal medication, such as a history of chronic rhinitis, nasal septal defect, cleft palate, nasal polyps, or nasal surgery other than cosmetic rhinoplasty.
  8. Use of hydroxychloroquine within the past 4 months, chloroquine with the past 9 months, or other investigational agents for COVID-19 within the past 30 days

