### **6.8 Contraception**

All female patients of childbearing potential must practice a highly effective method of contraception for 28 days after study drug administration. Male patients with partners of childbearing potential must practice a highly effective method of contraception for 45 days after study drug administration.

Highly effective methods of contraception include, but are not limited to, abstinence, sex only with persons of the same sex, monogamous relationship with a postmenopausal partner, monogamous relationship with vasectomized partner, vasectomy, licensed hormonal methods, intrauterine device, or consistent use of a barrier method (eg, condom, diaphragm) with spermicide.

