#### **8.1.3 *Pregnancy Testing (Females of Childbearing Potential Only)***

A urine pregnancy test is to be performed for female patients of childbearing potential at Screening. Results must be available and confirmed to be negative before study drug administration.

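### Inclusion criterion 5 defines childbearing potential two ways, so the pre-dose pregnancy test is required for women in monogamous same-sex relationships under the protocol synopsis but not under Section 5.2

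*Protocol*

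**What the plan says.** Criterion 5 appears twice in the protocol. In the synopsis (Inclusion Criteria), the women exempted from childbearing potential are the permanently sterile and those who are postmenopausal: "or postmenopausal [12 months with no menses without an alternative medical cause". In Section 5.2 the parenthesis carries on to a third exempt group: "postmenopausal [12 months with no menses without an alternative medical cause] or in monogamous same-sex relationships".

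The same two requirements follow in both places and apply only to women of childbearing potential. One is a negative urine pregnancy test at Screening. The other begins "Willingness to practice a highly effective method of contraception" and runs for 28 days after dosing.

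Other places rely on the term without defining it:
- Protocol Section 8.1.3: "A urine pregnancy test is to be performed for female patients of childbearing potential at Screening".
- Protocol Table 1, note a: "For women of child-bearing potential only. Results must be available and confirmed to be negative before study drug administration".
- Protocol Section 6.8: "All female patients of childbearing potential must practice a highly effective method of contraception for 28 days after study drug administration".
- SAP Section 6.1.3 and SAP Table 2, note a, which repeat the testing rule.

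Section 6.8 also lists the accepted contraception methods, among them "abstinence, sex only with persons of the same sex, monogamous relationship with a postmenopausal partner". The same list stands in both versions of criterion 5. Separately, Exclusion criterion 1 bars "Pregnant or lactating women or planning to conceive a child during the next 3 months".

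**The concern.** An eligibility term that decides who is tested for pregnancy before receiving an investigational vector product should have one meaning. Here a premenopausal, non-sterile woman in a monogamous same-sex relationship must be tested under one current text and need not be under the other. Two sites could therefore handle the same patient differently, each following a current version of the criterion.

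What is at stake is an unrecognised pregnancy at dosing. Being in a same-sex relationship now says nothing certain about a conception that has already happened. The protocol otherwise treats the test as a safeguard separate from the exclusion of pregnant women, with the result to be in hand before study drug is given. Section 5.2 leaves that safeguard unmandated for this one subgroup.

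**Working it through.** The plan states no figure on this point, so there is none to reproduce. The check is a comparison of texts, followed by a rough count.

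**Step 1. Read the two definitions.** In Section 5.2 the negation has to cover all three listed groups. If it covered only the first, postmenopausal women would count as being of childbearing potential. So Section 5.2 has three exempt groups and the synopsis has two.

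**Step 2. Apply both to the same patient** (premenopausal, not sterile, in a monogamous same-sex relationship).

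| Requirement | Synopsis | Section 5.2 |
|---|---|---|
| Of childbearing potential? | Yes | No |
| Negative urine test at Screening | Required | Not required |
| 28-day contraception condition | Required, ordinarily met by same-sex-only activity | Not required |
| Barred if pregnant (Exclusion 1) | Yes, no test prescribed | Yes, no test prescribed |

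The test is the only row with a practical difference.

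**Step 3. Look for a tie-breaker.** SAP Section 4.3 sends the reader to Protocol Sections 5.2 and 5.3 for the criteria. SAP Section 9.13 ranks the SAP above the protocol, but the SAP has no definition of its own and the clause does not address synopsis against body.

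**Step 4. Size.** Inputs from the protocol: 96 patients, 1:1 randomization, and ages 18 to 49 capped at about 30% of either arm (synopsis, Sections 6.2 and 10.3.1). Assumptions not in the documents: half of patients in each age band are women, none of those aged 18 to 49 is sterile, the cap is reached, and 1% to 5% of the women counted are in such relationships.

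- Women aged 18 to 49: 96 × 0.30 × 0.5 = 14.4.
- Expected affected: 14.4 × 0.01 = 0.144, to 14.4 × 0.05 = 0.72.
- In the NasoVAX arm: half of these, 0.072 to 0.36.
- Sensitivity, also counting 10% of women aged 50 and above (assumed): 96 × 0.70 × 0.5 = 33.6, of whom 3.36; total 14.4 + 3.36 = 17.76; affected 0.178 to 0.888.

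**Step 5. From enrolment to harm.** The chance that at least one such woman is enrolled is 1 − (1 − 0.0015)^96 = 0.134 to 1 − (1 − 0.0075)^96 = 0.515, where 0.0015 = 0.30 × 0.5 × 0.01 and 0.0075 = 0.30 × 0.5 × 0.05. The harm also needs an unrecognised pregnancy in that woman and a site that does not test her. If q is the probability of the first, the expected number of pregnant women dosed is at most 0.144q to 0.72q. The documents give no value for q.

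**The case against.** The case for leaving this alone is fairly strong. Section 5.2 is the full criteria section, the SAP points to it, and the natural reading is that it governs over a summary; Sections 6.8 and 8.1.3 would simply inherit its definition. Exclusion 1 bars pregnant women and those planning to conceive, a complete medical history is taken (Section 8.1.2), and pregnancies after dosing are followed to outcome (Section 9.6.4). A site that tests every premenopausal, non-sterile woman satisfies both texts. Adding the exemption to the synopsis would remove the inconsistency just as well.

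Much of this stands, and it keeps the point small. It does not remove it. If Section 5.2 governs, the subgroup goes untested by design and the synopsis is wrong, so one text must still change. Exclusion 1 and a history depend on the pregnancy being known. The direction of the fix is a choice: the contraception list appears beside both definitions and does not show what the sponsor intended. Deletion is preferable because it keeps the safeguard.

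Three stronger readings are not supported. A reader might infer that Section 5.2 drops the pregnancy test; it contains the test and omits one narrow subgroup. A reader might infer that contraception protection is lost as well; for these women the condition is ordinarily met already, so at most an affirmation is missing. A reader might take 13% to 51% as the risk of dosing a pregnant woman; it is the chance of enrolling at least one woman in the subgroup, and the harm is far less likely.

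**Conclusion.** The inconsistency is real, in current text, and not resolved by any clause in the protocol or SAP. Its operative content is one pre-dose urine pregnancy test for one narrow subgroup. Fewer than one affected patient is expected, given the assumed sex split and 1% to 5% prevalence; the count scales directly with both. The chance of a pregnant woman being dosed because of it is much lower than the chance of enrolling such a woman, and cannot be quantified from the documents. Endpoints, analysis sets, randomization and statistical analysis are unaffected. It rates as a minor safety-screening inconsistency.

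**What to change.** At the next amendment, delete from Section 5.2 criterion 5 the exemption for women in monogamous same-sex relationships, so that it matches the synopsis and the existing test applies to every premenopausal, non-sterile woman. A pointer to that single definition in Protocol Sections 6.8 and 8.1.3 and Table 1 note a, and in SAP Section 6.1.3 and Table 2 note a, would be tidy but is optional.

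The cost is one deleted phrase and, in expectation, about one extra urine test or fewer, using a test the trial already performs. That is an expectation and not a ceiling. The women concerned would also affirm an accepted contraception method, which imposes no new measure on them.
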